7.2. Participant Discontinuation/Withdrawal from the Study

To minimize the amount of missing data and to enable assessment of study objectives as planned in the study protocol, every attempt will be made to keep participants in the study irrespective of the following:

- adherence to or discontinuation from study drug
- adherence to visit schedule
- missing assessments
- study drug discontinuation due to AE
- development of comorbidities
- development of clinical outcomes

The circumstances listed above are *not* valid reasons for discontinuation from the study.

Participants will be withdrawn from the study in the following circumstances:

- enrollment in any other clinical study involving an IP or enrollment in any other type of medical research judged not to be scientifically or medically compatible with this study
- participation in the study needs to be stopped for medical, safety, regulatory, or other reasons consistent with applicable laws, regulations, and Good Clinical Practice (GCP)
- participant requests to be withdrawn from the study and clearly indicates that there will be no further contact of any kind with the site

Participants who agree to provide information relevant to any trial endpoint at the end of the study are not considered to have discontinued from the study.

A participant may withdraw from the study:

- at any time at his/her own request
- at the request of his/her designee (for example, parents or legal guardian)

- at the discretion of the investigator for safety, behavioral, compliance, or administrative reasons
- if the participant becomes pregnant during the study
- if enrollment in any other clinical study involving an investigational product or enrollment in any other type of medical research judged not to be scientifically or medically compatible with this study
- if the participant, for any reason, requires treatment with another therapeutic agent that has been demonstrated to be effective for treatment of the study indication, discontinuation from the study occurs prior to introduction of the new agent.

Discontinuation is expected to be uncommon.

When discontinuing from the study prior to Visit 21 or Visit 99, an early discontinuation visit should be conducted if possible, as described in the Schedule of Activities. See Schedule of Activities for data to be collected at the time of study discontinuation and follow-up and for any further evaluations that need to be completed. The participant will be permanently discontinued both from the study intervention and from the study at that time.

If the participant withdraws consent for disclosure of future information, the sponsor may retain and continue to use any data collected before such a withdrawal of consent. If a participant withdraws from the study, he/she may request destruction of any samples taken and not tested, and the investigator must document this in the site study records.

Participants discontinuing from the study prematurely for any reason should complete AE and other safety follow-up per Section 1.3 (Schedule of Activities), Section 8.3 (Adverse Events and Serious Adverse Events), and Section 8.2 (Safety Assessments) of this protocol.

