Abbreviations: BP = blood pressure; C-SSRS = Columbia-suicide severity rating scale; CT = computed tomography; ECG = electrocardiogram; EQ-5D-5L = EuroQol - 5 Dimension - 5 Level; HbA1c = glycated hemoglobin; hsCRP = high-sensitivity C-reactive protein; IWQOL-Lite-CT = Impact of Weight on Quality of Life-Lite-Clinical trials version; MRI = magnetic resonance imaging; MRI-PDFF = magnetic resonance imaging - proton density fat fraction; NAFLD = non-alcoholic fatty liver disease; NASH = nonalcoholic steatohepatitis; OGTT = oral glucose tolerance test; PHQ-9 = Patient Health Questionnaire-9; PR = pulse rate; SF-36v2 = Short-Form 36-item Health Survey Version 2; TNFα = tumor necrosis factor-α; VAS = visual analog scale.

Protocol I8F-JE-GPHZ(b)

Table 3. Study Period III- Early Discontinuation and Follow-Up Period

Activity	Early Discontin	nuation and Follow-U	Comment			
Visit Number	99	ED	801	At ED visit, participants who are unable or unwilling to continue the study treatment for any reason will perform an ED visit. If the participant is discontinuing during an unscheduled visit or a scheduled visit, that visit should be performed as the ED visit. At Visit 801, for participants who discontinue or complete the study within 72 weeks, Visit 801 (safety follow-up visit) should be performed 4 weeks after the last visit during the 72-week treatment period.		
Weeks of treatment	72		4 weeks post end of treatment period			
Allowable duration (days)	±7		±7	The visit date after randomization visit is determined in relation to the date of the randomization visit (± the allowed visit window).		
Fasting visit	X	X	X	If the participant is not fasting, the participant should be called in for a new visit within the visit window.		
Adverse events and product complaints	X	X	X			
Hypoglycemic events	X	X	X			
Concomitant medications	X	X	X			
Lifestyle management counseling		X		Counselling on diet and exercise, to be performed by a dietician or equivalent qualified delegate, will include calculation of individualized energy requirement and methods to change dietary composition and amount of physical activity. The lifestyle management counseling may be delivered on a separate day from the rest of that visit's study procedures but must occur within the visit window.		
Review diet and exercise goals		X				
Participant returns study drugs and injection supplies		X				

Activity	Early Discontin	uation and Follow-U	Comment			

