6.3. Measures to Minimize Bias: Randomization and Blinding

Interactive web-response system

All participants will be randomly assigned to study intervention using a central interactive-web response system (IWRS) at the end of Visit 3 after participant's eligibility is confirmed. Before the study is initiated, the log in information and directions for the IWRS will be provided to each site. Study intervention will be dispensed at the study visits summarized in the Schedule of Activities (Section 1.3).

The randomization will be stratified by

- baseline IGT (yes or no)
- baseline hyperlipidemia (yes or no)
- baseline NAFLD (yes or no), and
- sex

Blind break

Investigators, site staff, clinical monitors and participants will remain blinded to the treatment assignments until the study is complete.

The IWRS will be programmed with blind-breaking instructions. In case of an emergency, the investigator has the sole responsibility for determining if unblinding a participant's intervention assignment is warranted. Participant safety must always be the first consideration in making such a determination. If a participant's intervention assignment is unblinded, the sponsor must be notified immediately after breaking the blind. The date and reason that the blind was broken must be recorded in the source documentation.

If an investigator, site personnel performing assessments, or participant is unblinded, the participant must be discontinued from the study. In cases where there are ethical reasons to have the participant remain in the study, the investigator must obtain specific approval from a Lilly clinical research physician (CRP) and/or clinical research scientist (CRS) for the participant to continue in the study.

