7.1. Discontinuation of Study Intervention

In rare instances, it may be necessary for a participant to permanently discontinue (definitive discontinuation) study intervention. If study intervention is definitively discontinued, the participant will remain in the study to be evaluated for all planned efficacy and safety measurements. See the Schedule of Activities for data to be collected at the time of discontinuation of study intervention and follow-up and for any further evaluations that need to be completed.

Possible reasons leading to permanent discontinuation of IP:

• participant decision

o the participant requests to discontinue IP

• clinical considerations

- o initiation of GLP-1R agonist or DPP-4 inhibitor, if participants will not or cannot discontinue them
- o intolerable GI symptoms despite management as described in Section 10.8
 - *Note:* If intolerable GI symptoms persist despite symptomatic treatment, temporary drug interruption, and resumption at a lower dose of study intervention, the participant should be discontinued from the study intervention.
- o BMI ≤18.5 kg/m² with clinically significant health condition is reached at any time during the treatment period

Note: The investigator should contact the sponsor CRP and/or CRS to discuss whether it is medically appropriate for the participant to continue study treatment.

- o diagnosis of type 1 diabetes mellitus
- o diagnosis of medullary thyroid cancer after randomization
- o significant elevation of calcitonin (Section 10.4.7.3)
- o diagnosis of acute or chronic pancreatitis
- diagnosis of an active or untreated malignancy (other than basal or squamous cell skin cancer, in situ carcinomas of the cervix, or in situ prostate cancer) after randomization
- o development of any significant study intervention-related hypersensitivity reaction
- o onset of pregnancy in a female participant
- occurrence of any other treatment-emergent adverse event (TEAE), SAE, or clinically significant finding for which the investigator believes that permanent study intervention discontinuation is the appropriate measure to be taken
- o inadvertent enrollment if continued treatment with study intervention would not be medically appropriate (Section 7.2.1)
- o PHQ-9 score ≥15

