9.1. Statistical Hypotheses

The alternative hypotheses for the primary objective are the following:

- H_{10} : QW tirzepatide 10 mg is superior to placebo for percent change in body weight from randomization AND percentage of participants who achieve $\geq 5\%$ body weight reduction at 72 weeks.
- H₁₅: QW tirzepatide 15 mg is superior to placebo for percent change in body weight from randomization AND percentage of participants who achieve ≥5% body weight reduction at 72 weeks.

The above 2 hypotheses will be tested in parallel, each at a 2-sided significance level of 0.025.

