9.2. Sample Size Determination

Approximately, 348 participants will be screened to achieve 261 randomly assigned to study intervention (approximately 87 participants per intervention group).

The sample size determination assumes that evaluation of superiority of tirzepatide 10 mg and tirzepatide 15 mg to placebo will be conducted in parallel, each at a 2-sided significance level of 0.025 using a 2-sample t-test. Additionally, a difference of at least 11% mean body weight percentage reduction from randomization at 72 weeks for tirzepatide 10 mg and/or tirzepatide 15 mg compared with placebo, a common SD of 10%, and a dropout rate of 25% are assumed for statistical power calculations. Under the assumptions above, randomizing 261 participants in a 1:1:1 ratio to tirzepatide 10 mg, tirzepatide 15 mg, and placebo provides more than 90% power to demonstrate superiority of each tirzepatide dose to placebo.

The chosen sample size and randomization ratio also provides >90% power to establish superiority of tirzepatide 10-mg and/or tirzepatide 15-mg doses to placebo in terms of proportion of participants achieving at least 5% body weight reduction at 72 weeks, conducted in parallel using a Fisher's exact test, each at a 2-sided significance level of 0.025, assuming 25% of placebo-treated participants and 90% of tirzepatide-treated participants achieve the goal and a dropout rate of 25%.

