# 3. Analysis Sets

For purposes of analysis, the following populations are defined:

Table GPHZ.3.1. Description of Analysis Populations

Population	Description
Entered	All participants who sign informed consent form (ICF)
Randomized	All participants who are randomly assigned a study drug.
Modified Intent-to-Treat (mITT)	All randomly assigned participants who are exposed to at least 1 dose of study drug. Participants will be included in the treatment group to which they were randomized.

Table GPHZ.3.2. Description of Analysis Datasets

Analysis Datasets	Description
Efficacy Analysis Set (EAS)	Data obtained during the treatment period from the modified intent-to-treat (mITT) population, excluding data after discontinuation of study drug (last dose date + 7 days)
	Regarding imaging measurements (MRI and CT), data obtained during the treatment period from the mITT population, excluding data after discontinuation of study drug (last dose date + 14 days)
Full Analysis Set (FAS)	Data obtained during treatment period from the mITT population, regardless of adherence to study drug.
Safety Analysis Set (SS)	Data obtained during the treatment plus follow up period from the mITT population, regardless of adherence to study drug.

Unless otherwise specified, for analyses guided by the "efficacy" estimand, EAS will be used. For analyses guided by the "treatment-regimen" estimand, FAS will be used. For safety analysis, SS will be used.

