#### 4.3.3. Supplementary analyses

#### 4.3.3.1. Analysis Related to the Treatment Regimen Estimand

The analysis related to the "treatment-regimen" estimand will be conducted using data in the FAS.

The analysis for the mean percent change in body weight will be conducted utilizing ANCOVA. The response variable for the ANCOVA model will be percent change in body weight from randomization to Week 72. This model will include terms of baseline IGT (yes or no); baseline hyperlipidemia (based on TG; yes or no); baseline NAFLD (yes or no) and sex (female, male) as fixed effects and baseline body weight as a covariate. The ANCOVA analysis will be conducted with multiple imputation of missing body weight at Week 72 and statistical inference over multiple imputation of missing data guided by Rubin (1987).

With the aid of the ANCOVA model, 2-sided 95% CI for mean change in percent body weight from baseline to the 72-week visit between tirzepatide 10 mg or 15 mg QW and placebo will be derived.

With the aid of the logistic regression model, 2-sided 95% CI and odds ratio for percentage of participants achieving at least 5% body weight reduction from baseline to the 72-week visit between tirzepatide 10 mg or 15 mg QW and placebo will be derived.

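### As written, the supplementary treatment-regimen analysis does not reliably deliver its treatment-policy estimand: retention rules conflict, Visit 99 weights are not secured for analysis, and the SAP's ANCOVA omits treatment

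*Protocol*

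**What the plan says.** SAP 1.1.2.2 handles stopping study drug by a treatment-policy strategy. The passages that decide whether the Week 72 weights exist and are used are these.

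- **Protocol 7.1.** After permanent discontinuation of study drug, "the participant will remain in the study to be evaluated for all planned efficacy and safety measurements". One listed reason for stopping is starting a GLP-1R agonist or DPP-4 inhibitor that the participant will not or cannot stop.
- **Protocol 7.2.** Stopping drug is not a valid reason to leave the study. If another agent effective for the indication is required, however, "discontinuation from the study occurs prior to introduction of the new agent"; this stands in the list of ways a participant may withdraw. Someone who agrees to give endpoint information at the end is not counted as having left. Yet a person leaving before Visit 21 or Visit 99 is described as permanently out of both drug and study.
- **Protocol 6.3.** On unblinding, "the participant must be discontinued from the study", unless the sponsor approves continuation for ethical reasons.
- **Protocol 1.3, Table 3**, titled "Study Period III- Early Discontinuation and Follow-Up Period". It contains Visit 99, at 72 weeks ±7 days after randomization, to which people leaving early are asked to return, mainly for weighing. Appendix 14 names Visit 99 beside Visit 21 as the primary endpoint visit.
- **FAS (SAP Section 3; Protocol 9.3 to the same effect).** "Data obtained during treatment period from the mITT population, regardless of adherence to study drug". No dates are given for the treatment period.
- **SAP 4.1.** Participation ends at the earliest of death, withdrawal or Visit 801. Later data are excluded from analysis.
- **SAP 4.3.3.1.** The ANCOVA sentence begins "This model will include terms of baseline IGT (yes or no" and continues with the other stratification factors and baseline weight. Treatment is not listed. Confidence intervals for each dose against placebo are to come from this model.

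**The concern.** A treatment-policy estimand counts what happens after drug is stopped, including after a switch to another weight-lowering agent. If switchers and unblinded participants leave and are not weighed at Week 72, their values are imputed from same-arm participants who were measured after stopping drug (SAP 4.3.3.2), and those donors may not have switched. If Visit 99 weights are collected but then excluded, the donor pool shrinks and the placebo-based fallback becomes more likely. This is the sensitivity analysis that Protocol 9.4.3.1 sets beside a primary analysis resting on a hypothetical strategy, so its credibility matters even though it carries no alpha.

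**Working it through.** **1. The plan's own figures (primary analysis).** Protocol 9.1: "The above 2 hypotheses will be tested in parallel, each at a 2-sided significance level of 0.025". Alpha: 0.025 + 0.025 = 0.05. Protocol 9.2 assumes "a difference of at least 11% mean body weight percentage reduction from randomization at 72 weeks", SD 10, 87 per arm and 25% dropout. Evaluable per arm: 87 × 0.75 = 65.25, taken as 65. Noncentrality: 11 / (10 × √(2/65)) = 6.27. Power by noncentral t is 99.996%. For responders at 25% against 90%, Fisher's exact test gives more than 99.99%. The stated figure of more than 90% is reproduced. None of these quantities depends on the FAS, Visit 99 or the SAP 4.3.3.1 model.

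**2. Retention rules side by side.**

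| Event | Stays in study | Leaves study |
|---|---|---|
| Stops drug | 7.1; 7.2 retention aim | Table 3 sends those who cannot or will not continue drug to the early discontinuation visit, and 7.2 ties that visit to leaving both drug and study |
| Starts a GLP-1R agonist | 7.1 (reason for stopping drug only) | 7.2, if the agent counts as effective for the indication |
| Unblinded | 6.3, with approval | 6.3, by default |

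The Protocol's background describes a GLP-1R agonist approved for weight management outside Japan, so one event can fall under both 7.1 and 7.2. Table 3 still asks for a Week 72 weight from people whom 7.2 describes as permanently out.

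**3. Visit 99 and the data cut-off.** By timing, Visit 99 belongs to a 72-week treatment period. By its place in the schedule, it belongs to Study Period III; Table 2 is the treatment-period table. The FAS wording does not choose. The cut-off bites harder. Table 3 places Visit 801 four weeks after the last treatment-period visit. Take, as an illustration, a last such visit at Week 24: Visit 801 falls at 24 + 4 = Week 28, and Visit 99 comes 72 − 28 = 44 weeks later. Under SAP 4.1 that weight is excluded. For someone who stops drug but stays to Week 72, Visit 801 falls at 72 + 4 = Week 76 and nothing is lost. The exposure is therefore among those who leave early and return.

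**4. Donor pool (assumed rates).** With 10% to 25% of 87 stopping drug and 25% to 75% of those weighed at Week 72, retrieved dropouts number from 87 × 0.10 × 0.25 = 2.2 to 87 × 0.25 × 0.75 = 16.3 per arm. SAP 4.3.3.2 sets no minimum; its example of an insufficient pool is non-convergence.

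**5. ANCOVA.** Without a treatment term, fitted means do not differ by arm at given covariates, so no dose-against-placebo contrast exists. Protocol 9.4.3.1 lists treatment, strata and baseline weight for both the ANCOVA and the logistic model. SAP 4.3.3.1 gives no logistic terms. SAP 4.9 records no change here, and SAP 4.4.2.1 does list treatment in another ANCOVA.

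**6. Possible size (assumptions, not document figures).** Shift = excess share switching on placebo × effect of the new agent missed by imputation.
- Shares of 2% to 10% and effects of 3 to 10 points: 0.02 × 3 = 0.06 to 0.10 × 10 = 1.0 point.
- A narrower pairing, 5% to 10% on placebo and 1% to 2% on tirzepatide with 6 to 8 points: (0.05 − 0.01) × 6 = 0.24 to (0.10 − 0.02) × 8 = 0.64 point.

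Against 11 points, 1.0 is about 9% and 0.64 about 6%. Both calculations assume that no switcher contributes a Visit 99 weight.

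**7. Power of the supplementary analysis (assumed).** If the 25% who stop lose half to all of the effect, the difference is 11 × (1 − 0.25 × 0.5) = 9.625 down to 11 × (1 − 0.25) = 8.25. Power at two-sided 0.025 is at least 99.9% with 87 per arm and 99.2% with 65. Power is not the issue.

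**The case against.** The strongest reply is that the protocol already asks for what is needed. Table 3 invites early leavers back for a Week 72 weight, 7.2 does not count those who give endpoint data as having left, the new-agent rule stands under the ways a participant may withdraw, and 6.3 has a route to stay. Sections 7.1 and 7.2 also address somewhat different cases: an agent already started, and one needed in future. All of this stands. A reader might infer that the analysis cannot deliver its estimand at all; the documents do not support that.

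A reader might also infer that Visit 99 lies outside the FAS. That goes too far. Visit 99 is timed at Week 72, Appendix 14 treats it as a primary endpoint visit, and the imputation plan presupposes off-drug weights. The wording is ambiguous, not exclusionary. Likewise, the missing treatment term is confined to one SAP sentence and reads as a drafting omission, since the same section requires dose comparisons.

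Finally, the switching rates are unsupported. The protocol expects discontinuation to be uncommon and describes few drug options for obesity in Japan. That switchers would mostly be poor responders is also an assumption. The placebo-based fallback would usually shrink the difference, so no net direction can be claimed.

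What the reply does not answer is the SAP 4.1 cut-off, the statement in 7.2 that leavers are permanently out, and a SAP model that, taken literally, cannot produce its stated output.

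**Conclusion.** The point holds in limited form. Followed literally, the text can discard Week 72 weights that the treatment-policy imputation needs, and it specifies an ANCOVA with no treatment effect to estimate. The retention passages conflict enough that sites could handle the same event differently. The documents give no basis for a numeric bias. On the assumed inputs above it is small against 11 points, and it applies only if switchers leave, are not weighed or have their weight excluded, and are imputed from people not on the new agent. The primary efficacy estimand, its alpha and its power are untouched. The corrections should be made because they are cheap and this analysis is the plan's stated check on a hypothetical-strategy primary.

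**What to change.** 1. **Protocol 6.3, 7.1, 7.2 and Table 3.** Reconcile these passages. Which rule applies to a new agent or to unblinding is for the sponsor to decide. Under any rule, state that the Week 72 (Visit 99) weight is sought unless consent is withdrawn.
2. **FAS (Protocol 9.3, SAP Section 3).** Define it as data through Week 72, including Visit 99, whether or not the participant is on drug.
3. **SAP 4.1.** Exempt Visit 99 from the exclusion of data after withdrawal or Visit 801.
4. **SAP 4.3.3.1.** Add treatment group to the ANCOVA, and state the logistic terms (treatment, stratification factors, baseline weight) to match Protocol 9.4.3.1.

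The cost is protocol and SAP wording and a few more Visit 99 contacts; the visit already exists.
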